14.4.3 Unanticipated Device Effect Reporting

All UADE/SADE/USADE **must be reported** to the Sponsor, via eCRF, **immediately upon awareness of event but no later than 72 hours** by the study site personnel. An investigator shall submit to the reviewing EC a report of any UADE occurring during an investigation according to EC requirements.

14.4.4 Events of Special Interest

All study device failure/malfunction must be reported to the Sponsor, via eCRF, as soon as possible, within 72 -hours by the study site personnel. If a device failure is detected or suspected, it should be documented on the eCRF, and the device returned according to the Sponsor's instructions.

The investigational device should be sent to appropriate R&D team or designated Quality engineer. Complaints related to non-investigational products manufactured and/or distributed by Biosense Webster, used during the procedure related to other devices (other than the study device under investigation), are to be reported according to current Biosense Webster procedures and other policies as necessary (i.e., institutional policies, EC policies, and local regulations). Investigators are instructed to return devices in accordance with current company procedures and other relevant regulations.

Event reporting to relevant CA's in accordance with the jurisdictional regulations will occur by the sponsor and/or by the investigator, depending upon the local requirements and will be done in EU per MDR 2017/745. Event reporting will be done through the Eudamed web form once fully functional. Until then, the template for the Clinical Investigation Summary Safety Report Form will be used (MDCG 2020-10/1 or next revisions).

A device deficiency related to a medical device not manufactured by Biosense Webster should be reported by the investigator to their respective manufacturer as per relevant regulation. Complaints related to non-Biosense Webster, Inc. products must be handled according to institutional policies, EC policies, and local regulations.

14.5 Safety Oversight

Safety oversight will be conducted as described in the Safety Management Plan. Aggregate safety data will be reviewed during enrollment by the study safety lead in order to promptly identify new issues or trends which may have an impact on the conduct of the study and/or subject safety. Under the rules as defined in the Safety Management Plan, safety events will be reviewed by the Safety Management Team which may recommend appropriate action(s) to ensure subject safety.

15 Administrative Responsibilities

15.1 Ethics Committee and Competent Authority Application

The CIP (or amendment[s]), ICF, and other applicable study related documents must be approved by the EC and CAs before enrollment of subjects. The application shall be submitted by means of the electronic system referred to in Article 73 (MDR [EU - 2020/561]), which shall generate a Union-Wide unique single identification number for the Clinical Investigation. Any additional requirement imposed by the EC or CA shall be discussed, agreed upon, and followed. A signed copy of the EC and CA approval letters addressed to the investigator must be submitted to Biosense Webster certifying study approval prior to subject enrollment. Biosense Webster and the EC must approve, in writing, any changes to the protocol that affect the rights safety and/or welfare of the subjects or may adversely affect the validity of the study. In countries with a centralized submission process, a single submission will be performed in order to obtain the joint opinion from EC and CA. This applies for the initial application and for substantial modifications.

In addition, Biosense Webster, Inc. is responsible for notifying the relevant CA of the intention to perform a clinical investigation under this CIP and ensure to get the official response/ approval before starting the clinical investigation. For all relevant communication in relation to the clinical investigation the Union-Wide unique single identification number shall be used as a reference.

15.2 Audits and Inspections

The sponsor and/or designee and/or CAs may contact the participating institution to inform the investigator of an upcoming audit/inspection. The investigator should immediately notify the sponsor of any CA audits/inspection at the study site. The audit/inspection can include the review of documents, facilities, records, and any other resources deemed by the authorities to be related to study.

16 Deviations from the Clinical Investigation Plan

The investigator is responsible for ensuring that the clinical investigation is conducted in accordance with the procedures and evaluations described in this CIP. The study monitors shall verify that the conduct of the study is in compliance with the currently approved CIP and applicable regulations and shall identify any issues of non-compliance with regulations or guidelines.

Issues of non-compliance include but are not limited to repeated CIP deviations; failure to obtain proper informed consent; non-conformance to EC requirements; failure to report AEs, product malfunctions and other product issues; and another non-conformance to GCP.

A deviation to the CIP is defined as an instance of failure to follow, intentionally or unintentionally, the requirements of the CIP (e.g., missed test or procedure, visit out of window, non-adherence to inclusion/exclusion criteria). Investigators are not allowed to deviate from the CIP. Waivers are prohibited for this clinical study. Deviations to the CIP will be monitored closely and will be reported per EC/CA requirement.

Under emergency circumstances, deviations from the CIP to protect the rights, safety and well-being of a subject may proceed without prior approval of the sponsor and EC. Such deviations shall be documented and reported to the sponsor and the EC as required.

All instructions described in this CIP are to be followed. If an amendment is required, it must be made in written form and receive approval from all persons and authorities who approved the original CIP. Administrative changes (do not affect subject's benefits/risks ratio) may be inserted with abbreviated approval. All amendments will be distributed to all original CIP recipients.

17 Investigational Product

17.1 Use of the Investigational Device and Investigator Experience

17.1.1 Training

Investigators selected to participate in the study will be experienced in intracardiac mapping and AF ablation. The training of applicable clinical site personnel will be the responsibility of the Sponsor. Prior to initiating subject enrollment at a site, appropriate study training will be provided. The study training includes following:

- All investigators who will be performing the ablation procedures for this study will be required to attend device and PF technology training in accordance with the physician training charter. Investigators will also undergo a didactic training, which includes detailed reviews of the study catheter and the results of preclinical studies completed. This training will occur prior to first treatment of the subject and will take 2 hours on average.

- To ensure uniform data collection and CIP compliance, the Sponsor will conduct a training session that will include reviewing the CIP, eCRF and data collection process, and the AE reporting process. This training will occur during the site initiation visit, prior to site activation and will take on average 3 to 4 hours. The sponsor will reinforce the training or provide clarification throughout the study, as needed.

17.1.2 Materials

TRUPULSE™ Generator

Biosense Webster, Inc. USA, is the legal manufacturer of the generator to be used in this study in a manner similar to standard, commercially approved Biosense Webster products.

Complete manufacturing records of each generator manufactured for human use during this study are maintained at the respective manufacturing location. Each generator is released for human use under a Confirmation of Conformity from Regulatory Affairs that will certify that the investigational generator conforms to the Essential Requirements for product release apart from those features, that are being investigated in this clinical investigation. And that, with regard to these aspects, every precaution has been taken to protect the health and safety of the patient.

STSF Catheter

Biosense Webster, Inc. USA, is the legal manufacturer of the catheters to be used in this study. There is no change to the approved manufacturing process to the THERMOCOOL SMARTTOUCH™ SF Catheter. An investigational label will be applied to the devices for use with the TRUPULSE™ Generator for this study.

17.2 Device Acquisition and Accountability

After obtaining a fully executed clinical trial agreement and appropriate CA/EC approvals, the study site will receive the necessary amount of study-related materials prior to commencement. Study-related devices (investigational and non-investigational) will be shipped to the site upon completion of required documentation. Investigational Study Devices will be labeled as “**Investigational Device**” and are only to be used for subjects enrolled in this clinical study.

The Sponsor will keep records of all investigational devices shipped to the site. Investigational site personnel are responsible for appropriate logging of devices received, verification of packing slip information (i.e., lot numbers and quantity shipped) and date and identifying that each device was used in the study and disposition information completed when returned to the Sponsor.

The Investigational Device Accountability Log shall record the following information:

- Date of receipt
- Person in receipt of the devices
- Quantity received
- Catalog number
- Serial/lot numbers
- Expiry Date
- Date device was used
- Subject ID on whom device was used
- Date of return
- Reason for return (i.e., used without incident, malfunction, expired, end of study, ...)

17.3 Device Returns

All investigational devices (used and unused) will be returned to the Sponsor's attention and per Sponsor's Instructions. The THERMOCOOL SMARTTOUCH™ SF Bi-Directional Navigation Catheter shall be returned to the below address. Device deficiencies should be properly documented on the eCRF. Any suspected malfunctioning device or device associated with an AE (device related or probably/ possibly device related) will undergo a thorough complaint analysis. All returned devices must be properly labeled with the study name, the subject identification number, date of issue, identified as a defective return, non-defective return, or AE (as applicable). All tracking information must be retained in the event the package has been lost and requires tracking. All investigational devices should be returned to:

ATTN: Complaints Lab
C. G Laboratories, Inc.
[name]
[name]

18 Clinical Monitoring

Clinical site monitoring is conducted to ensure that the rights and well-being of human subjects are protected, that the reported trial data are accurate, complete, and verifiable, and that the conduct of the trial is in compliance with the currently approved CIP /amendment(s), with GCP, and with applicable regulatory requirement(s). Each site will undergo periodic monitoring of the study, which involves a visit from a Sponsor representative, qualified to perform such visit. Monitoring visits may include, but are not limited to, the following:

- Adherence to the CIP
- Source documentation verification and accuracy of the eCRFs
- Verification that informed consent is being obtained for all subjects participating in the study in accordance with requirements described in the CIP
- Verification of completeness of the site file
- Verification of accuracy of all study logs such as the Delegation of Responsibility Log, etc.
- Compliance with applicable regulations
- Identification and action to resolve any issues or problems with the study.

Data are to be submitted promptly via e-CRF after collection. Missing or unclear data will be corrected as necessary throughout the trial. Biosense Webster will request further documentation such as physician and/or cardiac EP lab procedure notes when complications or malfunctions are observed and reported. Specific monitoring requirements are provided in the study specific monitoring plan.

19 Statistical Methodology

The Sponsor will be responsible for the overall analysis of data from this CIP. A separate Statistical Analysis Plan (SAP) will be written and approved prior to database lock. The SAP will describe all planned analyses based on the statistical design of this study and the subsequent data collected. A brief statistical overview of key statistical analyses is provided below.

19.1 Levels of Significance

Significance levels and the type-I error control for the final analyses of the primary endpoints are specified below in the applicable sections describing the analyses.

19.2 Sample Size Justification

Primary Safety Endpoint:

Based on a performance goal of 12% and assuming an anticipated primary safety event rate of 5% for the primary safety endpoint, a sample size of 135 subjects (with 5% missing data due to attrition) will provide above 80% power to reject the null hypothesis for the primary safety hypothesis test using a one-sided exact binomial test. The target significant level is 0.025.

Primary Effectiveness Endpoint:

Based on a performance goal of 90% and assuming an anticipated failure-free rate of 97% for the primary effectiveness endpoint, a sample size of 100 subjects will provide above 80% power to reject the null hypothesis for the primary effectiveness hypothesis test using a one-sided exact binomial test. The target significant level is 0.025.

Secondary Effectiveness Endpoint:

Based on a performance goal of 50% and assuming an anticipated failure-free rate of 65% for the secondary effectiveness endpoint, a sample size of 100 subjects (with 10% missing data due to attrition) will provide above 80% power to reject the null hypothesis test for the secondary effectiveness hypothesis using a one-sided exact binomial test. The target significant level is 0.025.

Total Sample size:

The sample size of this study is mainly driven by the hypothesis test for the primary safety endpoint. The total sample size for this study will be 135 subjects, based on the 135 subjects needed for the primary safety endpoint evaluation, 100 subjects for the primary acute effectiveness endpoint evaluation, and 100 subjects for the secondary effectiveness endpoint evaluation. A 5% attrition rate of the subjects for the primary safety endpoint and no attribution of the subjects for the primary effectiveness endpoints were assumed for the total sample size estimation.

A total of 135 evaluable subjects will be included in the study. Each of the four (4) subsets (NAE, CT/MRA, EE and PVI durability) will consist of 30 subjects and will be integrated within the study.

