7.1 Description of the Study Design

The study will be carried out as an interventional, prospective, multicenter, single-arm safety and effectiveness evaluation using the THERMOCOOL SMARTTOUCH™ SF (STSF) catheter in conjunction with the TRUPULSE™ Generator.

The study will enroll subjects with drug refractory, symptomatic PAF who are candidates for catheter ablation. Subjects who sign the Informed Consent Form (ICF) and who meet all eligibility criteria will be enrolled and treated with the STSF Catheter and the TRUPULSE™ Generator. A maximum sample size of 135 evaluable subjects is planned in the study. To ensure generalizability of study results, no more than 25% of the total enrollment in the study will be allowed at a single site. All study subjects will be followed-up for 12 months after study procedure.

For the purpose of characterization of safety and to provide an assessment of lesion durability of the investigational ablation system four (4) subsets will be embedded in the study; the Neurological Assessment (NA), a Cardiac Computed Tomography (CT) or Magnetic Resonance Angiogram (MRA) imaging (CT/MRA), an Esophageal Endoscopy evaluation (EE) and a PVI durability subset in a prospective manner. Each subset will consist of 30 subjects, who will undergo the index ablation procedure and additional neurological, PV, esophageal and PVI durability assessments. The same subjects will participate in all four (4) subsets.

All subjects will be evaluated prior to the procedure, prior to discharge, and post procedure at 7 days (Day 7-9), 1 month (Day 23-37), 3 months (Day 76-104), 6 months (Day 166-194), and 12 months (Day 335-379).

Planned statistical analyses of the endpoints and analysis populations are described in the Statistical Analysis section (section 19) of this clinical investigational plan and in the Statistical Analysis Plan (SAP).

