9.2 Handling of Participant Withdrawals or Termination

If a subject is removed or withdraws from the study, the date and reason for withdrawal will be recorded on the appropriate electronic Case Report Form (eCRF) and the applicable on-site source documentation. If the subject is withdrawn due to an AE or SAE, the Investigator should follow the subject until the AE/SAE has resolved or is considered stable.

If a subject is unable to return for an office/clinic visit or cannot be contacted by telephone, 3 separate telephone calls should be made to obtain subject related safety information. All attempts should be documented in the source documents. If the subject does not respond to the 3 telephone calls, then the investigator must send a certified letter to the subject. If the subject does not respond to the letter, then the subject will be considered "lost to follow-up" for the study.

Subjects who have signed the ICF but are later found not to be eligible PRIOR to insertion of the study catheter can be replaced. Replacement subjects will be recruited and enrolled following the same procedures as non-replacement subjects.

10 Responsibilities

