19.3 Analysis Sets

Safety Population Analysis Set (SP): The SP analysis set will consist of all enrolled subjects who have had insertion of the study catheter, regardless of energy delivery.

Modified Intention-To-Treat (mITT) Analysis Set: The mITT analysis set will consist of enrolled subjects who meet eligibility criteria and have had insertion of the study catheter.

Per Protocol (PP) Analysis Set: The PP analysis set will consist of subjects who satisfy the following criteria:

- Have undergone ablation using PF and/or RF energy via the investigational ablation system per CIP
- Are treated for the study-related arrhythmia
- Are enrolled and without major CIP deviation that would affect the scientific integrity of the safety and effectiveness, including but not limited to the following:
 - Subjects found not meeting eligibility criteria
 - Failure to check for entrance block for each targeted PV after adenosine/isoproterenol challenge.

- Use of the investigational ablation system outside the PV region. A CTI line for documented typical AFL identified prior to or during the procedure using investigational system or commercial RF devices to complete the procedure is allowed during index or repeat ablation procedure (within blanking). For the treatment of arrhythmia outside the PV region, using commercial RF devices to complete the procedure is allowed. However, subjects using commercial RF devices for the non-PV regions and/or CTI lines will be excluded from the 12-month effectiveness analysis.
- Missing all CIP specified electrocardiographic effectiveness monitoring

Neurological Assessment (NA) Analysis Set: The NA analysis set will include 30 subjects who have had pre-and post-index-ablation procedure MRI and neurological assessments completed. Subjects with no pre-index ablation procedure MRI assessment and no lesions observed on post-MRI assessment will be included for analysis.

Esophageal Endoscopy (EE) Analysis Set: The EE analysis set will include 30 subjects who have had a readable 1 to 3 days post index-ablation procedure esophageal endoscopy assessment.

Cardiac CT/MRA Analysis Set: The CT/MRA analysis set will include 30 subjects who have readable outcomes at baseline and 3 months.

PVI Durability Analysis Set: The PVI durability analysis set will include 30 subjects who have readable electro-anatomical mapping at index ablation procedure and 75 days (+/-15 days) post index ablation procedure.

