19.4.2 Subject Disposition

Disposition and accountability of the study subjects will be summarized descriptively for the subject categories defined as following,

Enrolled Subjects: Patients who sign the ICF.

Excluded Subjects: Subjects who are enrolled but never undergo insertion of the study catheter. Excluded subjects will be subjected to safety event reporting between ICF signature and date of exclusion. Subjects who signed the ICF but are found to be ineligible prior to insertion of the catheter are also considered as excluded.

Evaluable Subjects: All enrolled subjects who have the study catheter inserted.

Discontinued Subjects: Evaluable subjects who have the catheter inserted, but do not undergo ablation (i.e., no energy is delivered with the study catheter).

- Discontinued subjects will remain in follow-up for 3-months post catheter insertion.
- Discontinued subset subjects are not subjected to the additional subset assessments (esophageal, neurological, PV and PVI durability).

- If an SAE is reported for a discontinued subject, the subject will be followed until event resolution (with or without sequelae), stabilization, or until the event is adequately explained.

Lost to Follow-up Subjects: Evaluable subjects of which contact is lost after most recent visit (despite 3 documented attempts to contact the subject).

Withdrawn / Early Termination Subjects: Subjects who withdraw consent for study participation or are withdrawn by the investigator, are terminated from the study prior to completion of all follow-up visits.

Completed Subjects: Enrolled subjects who have not been excluded, discontinued, withdrawn, terminated early, or lost-to-follow-up from the study prior to the final study visit.

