19.4.6.1 Handling of Missing Data

- For the final primary safety analysis, if a subject does not have full 12 months of follow-up and the subject has had a PAE at any time during the follow-up, then the subject will be considered an event. If a subject does not have 12 months of follow-up but has at least 3 months of follow-up, then their last observed status will be carried forward for the 12-month safety endpoint as a conservative proxy. If a subject does not have at least 3 months of follow-up for the primary safety endpoint, then this subject will be excluded from the final primary safety analysis.

- For the final secondary effectiveness analysis, if a subject has an effectiveness failure at any time during the evaluation period, then the subject will be considered having an event. Subjects without an effectiveness failure who do not have full 12 months of follow-up will be excluded from the final effectiveness analysis.
- To investigate the robustness of the analysis result for the primary endpoints, several sensitivity analyses will be performed. Details on these analyses will be provided in SAP

20 Ethics and Protection of Human Subjects

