## 7.8 Handling of Missing Data

### 7.8.1 Primary Safety Endpoint

If a subject has had a PAE or is adjudicated by CEC as having a PAE, regardless subject's follow-up duration, the subject will be considered having an event. If a

subject's follow-up time is less than 3 months and the subject has not had a PAE, that subject will be excluded from the primary safety endpoint analysis.

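### Primary safety power of above 80% holds only if exactly 128 or 129 subjects are analysed with loss unrelated to outcome; under SAP 7.8.1 with 135 in the mITT set and all PAEs observed it is 76.5%, or 63.7% if 8 to 18 are excluded

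*Protocol*

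**What the plan says.** Protocol section 19.2, the Protocol summary (section 4) and SAP section 6 make the same statement for primary safety: "a sample size of 135 subjects (with 5% missing data due to attrition) will provide above 80% power". The inputs are a performance goal of 12%, a true rate of 5% and a one-sided exact binomial test at 0.025. Section 19.2 adds that this test mainly drives the sample size.

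The number is capped. Protocol 7.1 says "A maximum sample size of 135 evaluable subjects is planned in the study", and Protocol 19.4.2 defines evaluable as "All enrolled subjects who have the study catheter inserted". The test is run in the mITT set, which also requires eligibility: "The mITT analysis set will consist of enrolled subjects who meet eligibility criteria and have had insertion of the study catheter". Under Protocol 9.2, replacement is provided for subjects "later found not to be eligible PRIOR to insertion of the study catheter can be replaced"; nothing similar is given for ineligibility found after insertion.

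SAP 7.8.1 sets the missing-data rule. It opens "If a subject has had a PAE or is adjudicated by CEC as having a PAE" and counts such a subject as an event whatever the length of follow-up. Otherwise, if the subject's "follow-up time is less than 3 months and the subject has not had a PAE, that subject will be excluded" from the analysis. Protocol 19.4.6.1 also counts a subject with a PAE as an event, but its closing exclusion sentence is looser: "If a subject does not have at least 3 months of follow-up for the primary safety endpoint, then this subject will be excluded".

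**The concern.** The power statement treats 5% attrition as a plain reduction from 135 to 128 subjects, so that subjects with and without events are lost alike. SAP 7.8.1 does not lose subjects that way. Each exclusion takes away an event-free subject, so the number of observed events stays at what 135 subjects produce while the denominator falls.

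The planned count also sits at a peak of the exact test's sawtooth. One fewer analysed subject lowers the permitted number of events, and a few more dilute the power.

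What is at stake is the chance that a device with the assumed 5% event rate meets its safety goal. Study success requires that goal, and the secondary effectiveness test is reached only if both primary goals are met.

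**Working it through.** **Inputs.** Goal 12%, true rate 5%, one-sided level 0.025, N = 135 and 5% attrition (Protocol 19.2). Safety is shown if the upper limit of the exact two-sided 95% interval is below 12% (Protocol 19.4.4). Exclusion rule from SAP 7.8.1.

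**Event limit.** For n analysed, c(n) is the largest c with P(X ≤ c | n, 0.12) ≤ 0.025. This gives c = 7 for n = 117 to 127 and c = 8 for n = 128 to 135. The confidence-interval rule gives the same limits: the upper bound is 11.94% for 8/128 (pass), 12.03% for 8/127 (fail) and 12.28% for 9/135 (fail).

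**The plan's own figure.** 135 × 0.95 = 128.25, so 128 analysed. With c = 8, P(X ≤ 8 | 128, 0.05) = 80.8%. The stated figure reproduces.

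**Other analysed counts, loss unrelated to outcome.** Power = P(X ≤ c(n) | n, 0.05).

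| n analysed | Event limit | Power |
|---|---|---|
| 117 | 7 | 76.8% |
| 127 | 7 | 69.7% |
| 128 | 8 | 80.8% |
| 129 | 8 | 80.2% |
| 130 | 8 | 79.6% |
| 135 | 8 | 76.5% |

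From 100 to 135, only 128 and 129 exceed 80%. If the number analysed varies as Bin(135, 0.95), those two counts together have a probability of about 31%, and average power is 76.5%.

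**Under SAP 7.8.1.** Let m be the mITT size and d the number of event-free subjects excluded, with every PAE observed. The events still come from all m subjects, so power = P(X ≤ c(m − d) | m, 0.05).

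| m | d | Power | d | Power |
|---|---|---|---|---|
| 135 | 0–7 | 76.5% | 8–18 | 63.7% |
| 134 | 0–6 | 77.2% | 7–17 | 64.5% |
| 133 | 0–5 | 77.8% | 6–16 | 65.2% |
| 130 | 0–2 | 79.6% | 3–13 | 67.5% |

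For m from 117 to 135 and d from 0 to 19, power exceeds 80% only at (m, d) = (128, 0), (129, 0) and (129, 1). With m = 135 and each event-free subject lost at random with probability 5%, average power is 72.6%.

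**If some PAEs go unobserved.** Assumption: exactly 7 of 135 are lost, unrelated to PAE status, and a fraction f of their PAEs is missed. Take X1 ~ Bin(128, 0.05) and X2 ~ Bin(7, 0.05(1 − f)); the goal is met if X1 + X2 ≤ c(128 + X2). Power is 76.5% at f = 0, 77.6% at f = 0.25, 78.7% at f = 0.50 and 80.8% at f = 1. It reaches 80% only at f of about 0.81.

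**Type I error, m = 135.** P(X ≤ 8 | 135, 0.12) = 0.0146 with 0 to 7 excluded; P(X ≤ 7 | 135, 0.12) = 0.0061 with 8 to 18 excluded.

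**The case against.** The stated figure is not an arithmetic slip. It reproduces at 128, and treating attrition as unrelated to outcome is the usual planning convention. At the planned loss the shortfall from 80% is 3.5 points (80 − 76.5), less than the effect of modest uncertainty in the assumed rate: with 135 analysed and a limit of 8, power is 79.8% at a true rate of 4.8% and 84.4% at 4.5%. A jumping event limit is a feature of any exact binomial test. The 63.7% needs 8 to 18 exclusions, that is 8/135 = 5.9% to 18/135 = 13.3%, above the stated 5%.

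The mITT set may also be smaller than 135. If exclusions unrelated to outcome left 128 with no further loss, or 129 with at most one, the claim would hold. Some PAEs settle late, such as phrenic nerve paralysis judged at the 3-month visit, and could be missed in lost subjects.

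These points limit the finding but do not remove it. The convention is not the rule the SAP lays down for this endpoint. Eight exclusions are one more than the planned loss of about seven; with random 5% loss, eight or more of 135 would be lost about 36% of the time. Most PAE types count only within 7 days, before most attrition, and about 81% of lost subjects' PAEs would have to be missed to restore 80%. The worst-case, best-case and tipping-point analyses in SAP 7.6.1 concern the result and do not address planned power.

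**Conclusion.** The concern holds. The statement of above 80% is right only at 128 or 129 analysed with loss unrelated to outcome. If all 135 evaluable subjects are in the mITT set, all PAEs are observed and the true rate is 5%, SAP 7.8.1 gives 76.5% with up to 7 event-free exclusions and 63.7% with 8 to 18. The first figure covers the planned loss; the second applies once loss goes beyond it.

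The conclusion rests on the SAP rule, because the last exclusion sentence of Protocol 19.4.6.1 lacks the condition that the subject had no PAE. It also depends on the mITT size and on how many PAEs are observed, as worked through above. The effect is on power only. Type I error is controlled, so a positive safety result is not called into question.

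**What to change.** In Protocol section 4, Protocol 19.2 and SAP section 6, replace the primary safety power sentence with:

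> Performance goal 12%, one-sided exact binomial test at 0.025. The safety goal is met with at most 8 subjects with a PAE if 128 to 135 are analysed and at most 7 if 117 to 127 are analysed. At a true rate of 5%, power is 76.5% with 135 analysed; if loss is unrelated to outcome it is 80.8% at 128 and 69.7% at 127. If all 135 are in the mITT set, all PAEs are observed and missing data are handled per SAP 7.8.1, power is 76.5% with up to 7 event-free subjects excluded and 63.7% with 8 to 18 excluded.

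The cost is wording in three places and a lower stated power. The test, the significance level, the event limits, enrolment and data collection do not change. If the sponsor would rather keep a claim above 80%, 139 to 146 analysed would give 84.1% down to 80.4% with loss unrelated to outcome, but that exceeds the planned maximum of 135.
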